4.6.3 Study Discontinuation

The Sponsor has the right to terminate this study at any time. Reasons for terminating the study may include, but are not limited to, the following:

- The incidence or severity of adverse events in this or other studies indicates a potential health hazard to patients
- Patient enrollment is unsatisfactory

The Sponsor will notify the investigator if the Sponsor decides to discontinue the study.

4.6.4 Site Discontinuation

The Sponsor has the right to close a site at any time. Reasons for closing a site may include, but are not limited to, the following:

- Excessively slow recruitment
- Poor protocol adherence
- Inaccurate or incomplete data recording
- Non-compliance with the International Council for Harmonisation (ICH) guideline for Good Clinical Practice
- No study activity (i.e., all patients have completed the study and all obligations have been fulfilled)

5. ASSESSMENT OF SAFETY

5.1 SAFETY PLAN

The safety plan for patients in this study is based on clinical experience with Mircera in completed and ongoing studies. The anticipated important safety risks for Mircera are outlined below. Please refer to the Mircera Investigator's Brochure for a complete summary of safety information.

Several measures will be taken to ensure the safety of patients participating in this study. Eligibility criteria have been designed to exclude patients at higher risk for toxicities. Patients will undergo safety monitoring during the study, including assessment of the nature, frequency, and severity of adverse events. In addition, guidelines for managing adverse events, including criteria for dosage modification and treatment interruption or discontinuation, are provided below.

5.1.1 Risks Associated with Mircera

5.1.1.1 Hypertension and Hypertensive Encephalopathy

Observational studies and registry data show that more than half of children with CKD have high blood pressure based upon a casual blood pressure reading.

ESA treatment may increase blood pressure in patients with CKD, possibly due to effects on the vasoactive hormone axes. The role of blood viscosity remains uncertain.

During development trials in adults, hypertension was reported as an adverse event in 23.6% of patients receiving Mircera and 22.6% of patients receiving reference ESAs.

In Study NH19707, around 50% of patients had hypertension reported as a preexisting condition at baseline, and 58% of patients were receiving—or had previously received—antihypertensive and/or diuretic agents. During the core study, 13% of patients required an increase in antihypertensive treatment. Of 8 patients with hypertension reported as an adverse event during the core study, all had hypertension and/or had received antihypertensive therapy prior to enrollment.

Hypertensive encephalopathy describes a syndrome of neurological dysfunction induced by severe hypertension. Less than 1% of patients with hypertension experience a hypertensive crisis at any time. During clinical development studies in adults, hypertensive encephalopathy was reported in 0.3% of patients receiving Mircera and in 0.1% of patients receiving reference ESAs. No patients in Study NH19707 experienced hypertensive encephalopathy.

Instructions for recording blood pressure values and adverse events of high blood pressure and hypertension are provided in Section [5.3.5.6](#).

5.1.1.2 Anti-Erythropoietin Antibody-Mediated Pure Red Cell Aplasia

AEAB-mediated PRCA is a very rare adverse effect of ESA treatment, caused by the formation of AEABs that neutralize endogenous EPO. The condition is characterized by severe, progressive, refractory anemia, low reticulocyte count, and absent erythroid precursor cells in bone marrow. Patients typically develop ESA resistance following initial response to treatment, and become transfusion-dependent. No cases of AEAB-mediated PRCA have been observed in patients receiving Mircera during clinical trials. Cumulatively to 19 July 2016, there have been 8 cases of confirmed AEAB-mediated PRCA following exclusive use of Mircera in the postmarketing setting, all involving adult patients *with CKD*. Total cumulative exposure to Mircera is currently more than 1.5 million patient-years.

Detailed information on recognition and diagnosis of AEAB-mediated PRCA is provided in [Appendix 4](#).

5.1.1.3 Low Platelet Count

During development trials in adults, platelet values below $100 \times 10^9/L$ were observed in 9.7% of patients treated with Mircera versus 6.7% of patients treated with reference ESAs. The incidence of thrombocytopenia reported as an adverse event was similar in both groups (approximately 0.22% vs. 0.32%, respectively).

In Study NH19707, platelet count at baseline ranged from $80\text{--}518 \times 10^9/L$. Median platelet count decreased slightly during the core study period in both dose groups. No events of bleeding were reported in any patients in association with low platelet counts. Thrombocytopenia was reported as an adverse event in 2 patients, in both cases classified as mild.

Instructions for recording platelet count values and adverse events of low platelet count and thrombocytopenia are provided in Section [5.3.5](#).

5.1.1.4 Vascular Access Thrombosis

Vascular access thrombosis (VAT) is a frequent and potentially serious problem in HD patients. Arteriovenous grafts are at greater risk of VAT than fistulas. Other possible risk factors include high hematocrit, hypercoagulability, and decreased blood flow (e.g., due to low cardiac output, hypovolemia, hypotension, or compression). During development trials, events suggestive of VAT were reported in 13.2% of patients receiving Mircera and 11.6% of patients receiving reference ESAs. In Study NH19707 involving pediatric patients on HD, during the core period, 4 patients reported 5 events of VAT.

5.1.1.5 Stevens-Johnson Syndrome and Toxic Epidermal Necrolysis

There has been only one case of Stevens-Johnson Syndrome (SJS)/toxic epidermal necrolysis (TEN) in which available information was suggestive of a possible causal role of Mircera, based primarily on temporal course and reappearance of typical symptoms after re-challenge. No cases suggestive of SJS/TEN or other severe cutaneous adverse reactions caused by Mircera were observed during clinical trials.

5.1.2 Management of Patients Who Experience Adverse Events

5.1.2.1 Anti-Erythropoietin Antibody-Mediated Pure Red Cell Aplasia

ESAs should be discontinued in any patient with confirmed AEAB-mediated PRCA. The physician should investigate for the presence of anti-EPO and anti-Mircera antibodies and perform a bone marrow examination. An additional blood sample should also be stored for an anti-PEG antibody determination after the assay has been developed.

Patients must not be switched to another recombinant ESA because of the risk of cross-reactivity of antibodies with endogenous and all recombinant ESAs (see [Appendix 4](#) for further detailed information on recognition and management of AEAB-mediated PRCA).

5.2 SAFETY PARAMETERS AND DEFINITIONS

Safety assessments will consist of monitoring and recording adverse events, including serious adverse events and adverse events of special interest, performing protocol-specified safety laboratory assessments, measuring protocol-specified vital signs, and conducting other protocol-specified tests that are deemed critical to the safety evaluation of the study.

Certain types of events require immediate reporting to the Sponsor, as outlined in Section 5.4.

5.2.1 Adverse Events

According to the ICH guideline for Good Clinical Practice, an adverse event is any untoward medical occurrence in a clinical investigation subject administered a pharmaceutical product, regardless of causal attribution. An adverse event can therefore be any of the following:

- Any unfavorable and unintended sign (including an abnormal laboratory finding), symptom, or disease temporally associated with the use of a medicinal product, whether or not considered related to the medicinal product
- Any new disease or exacerbation of an existing disease (a worsening in the character, frequency, or severity of a known condition) (see Section 5.3.5.8 and Section 5.3.5.9 for more information)
- Recurrence of an intermittent medical condition (e.g., headache) not present at baseline
- Any deterioration in a laboratory value or other clinical test (e.g., ECG, X-ray) that is associated with symptoms or leads to a change in study treatment or concomitant treatment or discontinuation from study drug
- Adverse events that are related to a protocol-mandated intervention, including those that occur prior to assignment of study treatment (e.g., invasive procedures such as blood sampling, discontinuation of medications)

Kidney transplantation and routine diagnostic procedures/tests are not considered adverse events and should therefore not be recorded on an Adverse Event eCRF page.

The start of dialysis or the change in dialysis modality should not be considered an adverse event and should be recorded on a specific eCRF page (see Section 5.3.5.11).

5.2.2 Serious Adverse Events (Immediately Reportable to the Sponsor)

A serious adverse event is any adverse event that meets any of the following criteria:

- Is fatal (i.e., the adverse event actually causes or leads to death)
- Is life-threatening (i.e., the adverse event, in the view of the investigator, places the patient at immediate risk of death)

This does not include any adverse event that, had it occurred in a more severe form or was allowed to continue, might have caused death.

- Requires or prolongs inpatient hospitalization (see Section [5.3.5.12](#))
- Results in persistent or significant disability/incapacity (i.e., the adverse event results in substantial disruption of the patient's ability to conduct normal life functions)
- Is a congenital anomaly/birth defect in a neonate/infant born to a mother exposed to study drug
- Is a significant medical event in the investigator's judgment (e.g., may jeopardize the patient or may require medical/surgical intervention to prevent one of the outcomes listed above)

The terms "severe" (Section [5.3.3](#)) and "serious" are not synonymous. Severity refers to the intensity of an adverse event (e.g., rated as mild, moderate, or severe); the event itself may be of relatively minor medical significance (such as severe headache without any further findings). Seriousness is a regulatory criterion for adverse event reporting. It should be considered in determining whether a case needs to be reported as a serious adverse event or not (e.g., a headache may be severe in terms of interfering significantly with a patient's usual function but would not be classified as serious, unless it met one of the criteria for seriousness described above).

Severity and seriousness need to be independently assessed for each adverse event recorded on the Adverse Event eCRF.

Serious adverse events are required to be reported by the investigator to the Sponsor immediately (i.e., no more than 24 hours after learning of the event; see Section [5.4.2](#) for reporting instructions).

As an exception, the following serious adverse events, which are common in the dialysis population, will not be reported in an expedited manner if unrelated to study drug, but will be recorded as serious adverse events on the Adverse Event pages of the eCRF:

- Thrombosis of vascular access for HD
- Peritonitis due to PD

5.2.3 Adverse Events of Special Interest (Immediately Reportable to the Sponsor)

Adverse events of special interest are required to be reported by the investigator to the Sponsor immediately (i.e., no more than 24 hours after learning of the event; see Section 5.4.2 for reporting instructions). Adverse events of special interest for this study are as follows:

- Cases of potential drug-induced liver injury that include an elevated ALT or AST in combination with either an elevated bilirubin or clinical jaundice, as defined by Hy's Law (see Section 5.3.5.7)
- Suspected transmission of an infectious agent by the study drug, as defined below
Any organism, virus, or infectious particle (e.g., prion protein transmitting transmissible spongiform encephalopathy), pathogenic or non-pathogenic, is considered an infectious agent. A transmission of an infectious agent may be suspected from clinical symptoms or laboratory findings that indicate an infection in a patient exposed to a medicinal product. This term applies only when a contamination of the study drug is suspected.

5.3 METHODS AND TIMING FOR CAPTURING AND ASSESSING SAFETY PARAMETERS

The investigator is responsible for ensuring that all adverse events (see Section 5.2.1 for definition) are recorded on the Adverse Event eCRF and reported to the Sponsor in accordance with instructions provided in this section and in Sections 5.4–5.6. The investigator is also responsible for reporting medical device complaints (see Section 5.4.5).

For each adverse event recorded on the Adverse Event page of the eCRF, the investigator will make an assessment of seriousness (see Section 5.2.2 for seriousness criteria), severity (see Section 5.3.3), and causality (see Section 5.3.4).

5.3.1 Adverse Event Reporting Period

Investigators will seek information on adverse events at each patient contact. All adverse events, whether reported by the patient or noted by study personnel, will be recorded in the patient's medical record and on the Adverse Event eCRF.

After informed consent has been obtained but prior to initiation of study drug, only serious adverse events caused by a protocol-mandated intervention (e.g., invasive procedures such as blood sampling, discontinuation of medications) should be reported (see Section 5.4.2 for instructions for reporting serious adverse events).

After initiation of study drug, all adverse events will be reported until 28 days after the final dose of study drug.

Instructions for reporting adverse events that occur after the adverse event reporting period are provided in Section 5.6.

5.3.2 Eliciting Adverse Event Information

A consistent methodology of non-directive questioning should be adopted for eliciting adverse event information at all patient evaluation timepoints. Examples of non-directive questions include the following:

"How have you felt since your last clinic visit?"

"Have you had any new or changed health problems since you were last here?"

5.3.3 Assessment of Severity of Adverse Events

The World Health Organization (WHO) toxicity grading scale (see [Appendix 7](#)) will be used for assessing adverse event severity. [Table 4](#) will be used for assessing severity for adverse events that are not specifically listed or are not appropriate (e.g., due to the disease under study or age of the patient) in the WHO toxicity grading scale.

Table 4 Adverse Event Severity Grading Scale for Events Not Specifically Listed in WHO Toxicity Grading Scale

Grade	Severity
1	Mild; transient or mild discomfort (<48 hours); no medical intervention or therapy required
2	Moderate; mild to moderate limitation in activity; some assistance may be needed; no or minimal medical intervention or therapy required
3	Severe; marked limitation in activity; some assistance usually required; medical intervention or therapy required; hospitalization possible
4	Life-threatening; extreme limitation in activity; significant assistance required; significant medical intervention or therapy required, hospitalization or hospice care probable

Notes: Developed by the Division of Microbiology and Infectious Diseases.

Regardless of severity, some events may also meet seriousness criteria. Refer to definition of a serious adverse event (see [Section 5.2.2](#)).

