Proteinuria	1+ or <0.3% or <3g/L or 200 mg–1 g loss/day	2–3+ or 0.3–1.0% or 3–10 g/L 1–2 g loss/day	4+ or >1.0% or >10 g/L 2–3.5 g loss/day	nephrotic syndrome or >3.5 g loss/day
Hematuria	microscopic only	gross, no clots	gross + clots	obstructive or required transfusion
CARDIAC DYSFUNCTION				
Cardiac Rhythm		asymptomatic, transient signs, no Rx required	recurrent/persistent; no Rx required	requires treatment
Hypertension	transient increase >20 mm; no Rx required	recurrent, chronic, >20 mm, Rx required	requires acute Rx; no hospitalization required	requires hospitalization
Hypotension	transient orthostatic hypotension, no Rx	symptoms correctable with oral fluids Rx	requires IV fluids; no hospitalization required	requires hospitalization
Pericarditis	minimal effusion	mild/moderate asymptomatic effusion, no Rx required	symptomatic effusion; pain; EKG changes	tamponade; pericardiocentesis or surgery required
Hemorrhage, Blood Loss	microscopic/occult	mild, no transfusion	gross blood loss; 1–2 units transfused	massive blood loss; >3 units transfused

Appendix 7
WHO Toxicity Grading Scale for Determining the Severity of Adverse Events (cont.)

RESPIRATORY				
Cough	transient; no Rx	treatment-associated cough local Rx	uncontrolled	
Bronchospasm, Acute	transient; no Rx < 80%–70% FEV ₁ (or peak flow)	requires Rx normalizes with bronchodilator; FEV ₁ 50%–70% (or peak Flow)	no normalization with bronchodilator; FEV ₁ 25%–50% (or peak flow retractions)	cyanosis: FEV ₁ < 25% (or peak flow) or intubated
GASTROINTESTINAL				
Stomatitis	mild discomfort; no limits on activity	some limits on eating/drinking	eating/talking very limited	requires IV fluids
Nausea	mild discomfort; maintains reasonable intake	moderate discomfort; intake decreased significantly; some activity limited	severe discomfort; no significant intake; activities limited	minimal fluid intake
Vomiting	transient emesis	occasional/moderate vomiting	orthostatic hypotension or IV fluids required	hypotensive shock or hospitalization required for IV fluid therapy
Constipation	mild	moderate	severe	distensions w/vomiting
Diarrhea	transient 3–4 loose stools/day	5–7 loose stools/day	orthostatic hypotension or > 7 loose stools/day or required IV fluids	hypotensive shock or hospitalization for IV fluid therapy required

Appendix 7

WHO Toxicity Grading Scale for Determining the Severity of Adverse Events (cont.)

NEURO AND NEUROMUSCULAR				

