Neuro-cerebellar	slight incoordination dysdiadochokinesis	intention tremor, dysmetria, slurred speech; nystagmus	locomotor ataxia	incapacitated
Mood	mild anxiety or depression	moderate anxiety or depression and therapy required	severe anxiety or depression or mania; needs assistance	acute psychosis; incapacitated, requires hospitalization
Neuro control (ADL=activities of daily living)	mild difficulty concentrating; no Rx; mild confusion/agitation; ADL unaffected	moderate confusion/agitation some limitation of ADL; minimal Rx	severe confusion/agitation needs assistance for ADL; therapy required	toxic psychosis; hospitalization
Muscle strength	subjective weakness no objective symptoms/signs	mild objective signs/symptoms no decrease in function	objective weakness function limited	paralysis
OTHER PARAMETERS				
Fever: oral, > 12 hours	37.7°C –38.5°C or 100.0°F–101.5°F	38.6°C–39.5°C or 101.6°F–102.9°F	39.6°C–40.5°C or 103°F–105°F	> 40°C or > 105°F
Headache	mild, no Rx therapy	transient, moderate; Rx required	severe; responds to initial narcotic therapy	intractable; required repeated narcotic therapy
Fatigue	no decrease in ADL	normal activity decreased 25%–50%	normal activity decreased > 50% can't work	unable to care for self
Allergic Reaction	pruritus without rash	localized urticaria	generalized urticaria; angioedema	anaphylaxis

Appendix 7
WHO Toxicity Grading Scale for Determining the Severity of Adverse Events (cont.)

OTHER PARAMETERS continued				
Local Reaction	tenderness or erythema	induration < 10 cm or phlebitis or inflammation	induration > 10 cm or ulceration	necrosis
Mucocutaneous	erythema; pruritus	diffuse, maculopapular rash, dry desquamation	vesiculation, moist desquamation, or ulceration	exfoliative dermatitis, mucous membrane involvement or erythema, multiforme or suspected Stevens-Johnson or necrosis requiring surgery

NOTE: For coding purposes, the following toxicity grades may be used interchangeably: 1 = mild; 2 = moderate; 3 = severe; 4 = life threatening.

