#### **4.4.2 Adverse Events**

All AEs recorded in the CRF will be listed and classified by System Organ Class (SOC) and Preferred Term (PT). Events will be coded using the latest version of Medical Dictionary for Regulatory Activities (MedDRA). Adverse event severity will be graded according to the WHO Toxicity Grading Scale for determining the severity of adverse events (refer to Appendix 7 of the study protocol for details). AEs that occurred during the treatment period: from the first treatment dose until 28 days after last dose or until the final visit (whichever is latest) will be summarized. Standard safety analyses for all AEs, related AEs, serious AEs, fatal AEs and AEs leading to study drug modification or discontinuation or withdrawal from study will be performed in terms of frequency tables by event and patient.

All adverse events of special interest (AESI) will be presented. AESI include but are not limited to the following:

- Cases of potential drug-induced liver injury that include an elevated ALT or AST in combination with either an elevated bilirubin or clinical jaundice, as defined by Hy's Law (see Section 5.3.5.7 of study protocol)
- Suspected transmission of an infectious agent by the study drug, as defined below:

Any organism, virus, or infectious particle (e.g., prion protein transmitting transmissible spongiform encephalopathy), pathogenic or non-pathogenic, is considered an infectious agent. A transmission of an infectious agent may be suspected from clinical symptoms or laboratory findings that indicate an infection in a patient exposed to a medicinal product. This term applies only when a contamination of the study drug is suspected.

Adverse events related to covid-19 will be identified using the special covid-19 SMQ containing a narrow basket of preferred terms (PTs) to provide a more targeted list of events related to the SARS-CoV-2 virus. Only events occurring in the pandemic timeframe (1 Dec 2019 onwards) will be included in this list. A listing of such adverse events associated with covid-19 will be provided. For those patients with confirmed covid-19 infection or positive PCR test (9 preferred terms from the above SMQ) any other AEs occurring within  $\leq 7$  days before and  $\leq 30$  days after start date of the AE will also be considered as covid-19 associated events.

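### The fever row of the Appendix 7 severity scale assigns 40.1–40.5°C to both Grade 3 and Grade 4 in Celsius, but to Grade 3 only in Fahrenheit

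*Protocol*

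**What the plan says.** Protocol Section 5.3.3 states that the WHO toxicity grading scale in Appendix 7 "will be used for assessing adverse event severity". Table 4 in that section is the fallback for "adverse events that are not specifically listed or are not appropriate (e.g., due to the disease under study or age of the patient"). SAP 4.4.2 repeats the rule without mentioning the fallback: "Adverse event severity will be graded according to the WHO Toxicity Grading Scale for determining the severity of adverse events".

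The Appendix 7 row labelled "Fever: oral, > 12 hours" gives each grade in two units:

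- Grade 1: "37.7°C –38.5°C or 100.0°F–101.5°F"
- Grade 2: "38.6°C–39.5°C or 101.6°F–102.9°F"
- Grade 3: "39.6°C–40.5°C or 103°F–105°F"
- Grade 4: above 40°C, or above 105°F

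The closing note to Appendix 7 equates Grade 3 with severe and Grade 4 with life threatening.

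In the hemorrhage row of the same appendix, Grade 3 is "gross blood loss; 1–2 units transfused". Grade 4 pairs a massive-loss descriptor with more than 3 units.

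**The concern.** Grade bands should be exclusive, and limits printed in two units should describe the same temperature. At the boundary between Grades 3 and 4 the fever row does neither: the Celsius bands overlap, and the Celsius and Fahrenheit starting points for Grade 4 differ. The grade of one and the same fever can then depend on the thermometer's unit and on which cell the site reads.

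Occurrence and severity of adverse events is a stated safety endpoint (protocol Section 2, SAP 2.2.5), and protocol Section 6.5 summarizes severity on four points. Section 9.4 expects about 35 sites for about 40 patients, so most sites would grade very few children and have little chance to settle on a common practice. Use of both units across sites is an assumption. The study carries both an IND and a EudraCT number, which makes it plausible, but the documents do not state it. The Celsius overlap does not need that assumption.

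**Working it through.** **Inputs.** The four fever cells of Appendix 7, as given above.

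**Formulas.** °F = °C × 1.8 + 32, and °C = (°F − 32) / 1.8.

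**Step 1: are the two Grade 4 limits equivalent?**

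- 40 × 1.8 + 32 = 104.0°F, against the printed 105°F: a difference of 1.0°F.
- (105 − 32) / 1.8 = 40.56°C, against the printed 40°C: a difference of 0.56°C.

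They are not equivalent.

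**Step 2: which readings carry two grades?** Each reading to one decimal is graded in Celsius, then converted, rounded to 0.1°F and graded in Fahrenheit.

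| °C | °F | Grade in °C | Grade in °F |
|---|---|---|---|
| 40.0 | 104.0 | 3 | 3 |
| 40.1 | 104.2 | 3 and 4 | 3 |
| 40.2 | 104.4 | 3 and 4 | 3 |
| 40.3 | 104.5 | 3 and 4 | 3 |
| 40.4 | 104.7 | 3 and 4 | 3 |
| 40.5 | 104.9 | 3 and 4 | 3 |

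The Celsius Grade 3 band holds ten one-decimal readings (39.6 to 40.5). Five of them also meet Grade 4.

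**Step 3: which cell is out of line?** The Celsius Grade 3 ceiling is 40.5°C. The Fahrenheit Grade 3 ceiling and the Fahrenheit Grade 4 start are both 105°F, which is 40.56°C. These three entries agree to within 0.06°C. Only the Celsius Grade 4 start, at 40°C, does not fit.

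**Step 4: the rest of the row.** Single-reading mismatches between units occur at three lower points: 37.7°C (99.9°F) is Grade 1 in Celsius and ungraded in Fahrenheit; 38.6°C (101.5°F) is Grade 2 against Grade 1; 39.5°C (103.1°F) is Grade 2 against Grade 3. Each affects one 0.1°C step and puts no reading in two grades within one unit. They are of a different order from the five-reading overlap.

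**Step 5: the hemorrhage row.** The numeric parts are 1–2 units (Grade 3) and more than 3 units (Grade 4). Exactly 3 units meets neither number, so its grade rests on whether the loss is judged gross or massive. Protocol Section 4.4.3 has sites record the units transfused and report the indication as an adverse event, so the situation can arise in the data.

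**The case against.** The strongest reply is that little turns on this row, and most of that reply stands.

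- **Table 4.** A reader might infer that Table 4 never helps because fever is listed in Appendix 7. That is too strong. Section 5.3.3 also allows Table 4 where the WHO scale is not appropriate, for example because of age. The row is for oral temperature and the study enrolls from 3 months, so an investigator may reasonably use Table 4 for a very young child. For children in whom the row is appropriate, the overlap remains.
- **Fever in peritonitis.** This looks like the natural example in children on peritoneal dialysis. However, Section 5.3.5.2 asks for the diagnosis rather than its signs, so such a fever would usually be recorded as peritonitis. The row mainly matters for fever without a diagnosis, severe or serious secondary fever recorded separately (Section 5.3.5.3), and fever within 24 hours of an injection, which Section 5.3.5.1 records as its own sign.
- **Consequences.** A reader might infer from the life-threatening label that the grade drives expedited reporting, or that one re-graded child in 40 (1/40 = 2.5 percentage points) shifts a planned result. The documents support neither. Section 5.2.2 assesses seriousness independently of severity. Neither adverse event of special interest uses a fever grade, and the dose adjustments in Table 3 use hemoglobin. SAP 4.4.2 names no Grade 4 table in which the 2.5 points would appear. Temperature is not among the vital signs in Section 4.5.5, so the vital-sign endpoint is untouched.
- **A tie-break elsewhere.** Section 5.3.5.4 records the most extreme severity of a persistent event that worsens. That concerns change over time, not one reading that meets two grades. Nor does it help to apply both limits of the Grade 4 cell to every reading: a converted Fahrenheit value would then also meet both grades.
- **Hemorrhage.** A reader might infer that a 3-unit event cannot be graded at all. The gross and massive descriptors still allow a judgement. The gap is in the numbers only.

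**Conclusion.** The fever row is wrong as printed. Readings of 40.1–40.5°C meet Grades 3 and 4 in Celsius and Grade 3 alone in Fahrenheit, and neither document says which prevails. The result rests only on the printed limits and unit conversion.

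The practical size is small. It concerns oral fever of more than 12 hours, in a 0.5°C range, recorded as an event in its own right and graded on Appendix 7 rather than Table 4. The documents give no expected count of such events; few are likely. The point is worth correcting because severity is a stated safety endpoint and the ambiguity sits at the line between severe and life threatening.

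The hemorrhage cells are a lesser matter. The numeric gap at 3 units is real, but nothing in the documents shows whether 3 units belongs to Grade 3 or Grade 4.

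**What to change.** **Fever.** In Appendix 7, change the Celsius Grade 4 limit to above 40.5°C. It then meets the Grade 3 ceiling and agrees with both Fahrenheit entries: 40.5°C (104.9°F) is Grade 3 in both units, and 40.6°C (40.6 × 1.8 + 32 = 105.1°F) is Grade 4 in both. The mismatch between the Grade 4 limits falls from 0.56°C to 0.06°C. The three lower single-reading mismatches would remain and can be left.

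If amending the protocol is impractical, state the same convention in SAP 4.4.2 before database lock.

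**Hemorrhage.** Reconcile the Grade 3 and Grade 4 cells with each other, and with the source of the scale, so that exactly 3 units falls in one numeric band.

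**Cost.** The wording is a few table cells or one line of the SAP. Two further costs should be counted. A protocol amendment needs the approvals in Section 9.6. The SAP also post-dates the interim review of 12 September 2019, so events may already have been graded. Any fever graded in the 40.1–40.5°C range should be checked. Because temperature is not a scheduled assessment, the reading may have to come from the source records through a site query. No new patient assessments are needed.
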